#### **4.2.1      Justification for inclusion and exclusion criteria**

The criteria are set to minimize the risk to the volunteers, to ensure a subject population that will enable the investigation of the set objectives, to provide equal opportunity for inclusion and not to exclude subjects that may benefit directly from the trial.

#### **4.2.2      Criteria for discontinuation**

Subjects may be discontinued from study treatment and assessments at any time, at the discretion of the investigator. Specific reasons for discontinuing a subject from the study are:

1. Withdrawal of informed consent.
2. Development of exclusion criteria or other safety reasons during the study.
3. Protocol non-compliance.
4. Incorrect enrollment of the subject
5. Disease progression
6. Stem cell transplant

## 5. TREATMENT

The investigator will instruct the patient to take the study drugs as per protocol. All dosages prescribed and dispensed to the patient and any dose change or interruption must be recorded in the dosage administration record CRF, as appropriately.

This is an open-label dose escalation study using a 3+3 design. Before applying the dose escalation rules, 3 subjects in any given cohort must have completed the DLT observation period which is defined as 28 days (1 cycle) of therapy followed by evaluation for toxicity on Cycle 2 Day 1 (Study Day 29 +/- 3 days). The dose level in which 2 patients experience unacceptable toxicity is usually considered the maximum administered dose (MAD). We will define the MTD as the next lower dose level in which no more than 1/6 patients experience unacceptable toxicity. Dose escalation will cease if 2 or more patients develop DLT. There will be no intrapatient dose escalation.

Enrollment in a cohort will proceed as follows:

- If no dose limiting toxicity (DLT) is observed during the DLT observation period in the initial 3 subjects of a cohort, dose escalation to the next higher dose level cohort will occur.
- If 1 DLT is observed, 3 additional subjects will be enrolled at the same dose level for a total of at least 6 subjects. If no further DLT(s) are observed, escalation to the next higher dose level cohort will occur.

Dose escalation will occur at the planned dose levels until the MTD is determined or until the highest dose level is tested. The MTD is defined as the highest dose at which <33% of the subjects enrolled in a cohort experience a DLT. At least 6 subjects will be treated at the MTD or highest tested dose.

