## **2.1 PRIMARY**

- Define maximum tolerated dose (MTD) and /or recommended phase II dose for the combinations of venetoclax (ABT-199, GDC-0199) plus Ibrutinib (PCI-32765) and rituximab in Relapsed or Refractory DLBCL by assessing the incidence of dose limiting toxicities (DLTs) in first 29 days.

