### 5.1 DEFINITIONS OF DOSE-LIMITING TOXICITIES

**Incidence of Dose Limiting Toxicities (DLT).** Time frame: 28 days (1 cycle of therapy followed by laboratory evaluation for toxicity on Cycle 2 Day 1, Study Day 29) Toxicity will be assessed using the National Cancer Institute (NCI) Common Toxicity Criteria for Adverse Events (CTCAE), version 4.03

[http://ctep.cancer.gov/protocolDevelopment/electronic\\_applications/ctc.htm](http://ctep.cancer.gov/protocolDevelopment/electronic_applications/ctc.htm) unless otherwise specified. A DLT is defined as an adverse event or abnormal laboratory value assessed as at least possibly related to the study medication, that occurs  $\leq$  29 days or prior to the Cycle 2, Day 1 visit (whichever is longer) following the first dose, and meets any of the protocol-specified DLT criteria.

**Dose-limiting toxicity:** The dose-limiting toxicity described in this section refers to toxicity derived from any or all of the agents used in the combination regimen.

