#### Hematologic:

- Grade 3 neutropenia (ANC <1,000/mm^3) that does not resolve to  $\leq$  Grade 2 within 3 weeks with the use of growth factor

- Grade 4 neutropenia (ANC <500/mm^3)
- Febrile neutropenia (ANC <1,000/mm^3 with a fever  $\geq 38.3^{\circ}\text{C}$ )
- Grade 4 thrombocytopenia (<25,000/mm^3) that persists for  $\geq 7$  days, despite holding treatment
- Grade 3 thrombocytopenia associated with Grade  $\geq 2$  bleeding or requiring RBC or platelet Transfusions

Non-Hematologic:

- Any Grade 3 or higher non-hematologic adverse event where relationship to study drug(s) cannot be ruled out (Note: excludes rituximab infusion reactions)
- Grade  $\geq 3$  nausea, vomiting, or diarrhea uncontrolled by maximal supportive care and persisting greater than 7 days
- Grade 3 fatigue persisting for greater than 7 days
- Treatment delay of any drug greater than 7 days for toxicity

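### The escalation rule does not wait for an event that began in the DLT window and whose duration criterion is still open at Cycle 2 Day 1

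*Combined protocol and SAP*

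**What the plan says.** **Decision point.** Section 5 applies the escalation rules when "3 subjects in any given cohort must have completed the DLT observation period which is defined as 28 days (1 cycle) of therapy". The visit that closes this period is worded there as "evaluation for toxicity on Cycle 2 Day 1 (Study Day 29 +/- 3 days"). If the initial three patients show no DLT in that period, "dose escalation to the next higher dose level cohort will occur". One DLT leads to three more patients at the same level. The wording has no exception for an event still unresolved.

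**Attribution window.** The primary objective (Section 2.1) defines the MTD "by assessing the incidence of dose limiting toxicities (DLTs) in first 29 days". Section 5.1 counts a related event that occurs within "29 days or prior to the Cycle 2, Day 1 visit (whichever is longer) following the first dose" and that meets a listed criterion. It sets no date by which the criterion must be met.

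**Criteria with a clock.** Section 5.1, repeated in Section 12, includes:
- Grade 3 neutropenia that does not improve to at most "Grade 2 within 3 weeks with the use of growth factor";
- Grade 4 thrombocytopenia lasting at least 7 days although treatment is held;
- "Treatment delay of any drug greater than 7 days for toxicity";
- Grade 3 or higher nausea, vomiting or diarrhea, and Grade 3 fatigue, each lasting more than 7 days.

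**Related rules.** Table 1 of Section 7.1.4 holds venetoclax for Grade 3 or 4 neutropenia until recovery to Grade 2 or better. Section 8.1.1 makes a required platelet transfusion in the DLT period a DLT. Section 8.1.3 prohibits hematopoietic growth factors in that period.

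**The concern.** A duration criterion cannot be met on the day an event starts. If the event starts late in Cycle 1, the Cycle 2 Day 1 evaluation finds a patient who has an open event but no DLT so far. Section 5 then calls for escalation.

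Two things are at stake. The planned step doubles the venetoclax dose from 400 to 800 mg, so new patients may start the higher level while a DLT at the lower one is still maturing. And with cohorts of three to six, one event decides the outcome. At the top level the same gap affects the MTD declaration and the opening of an expansion cohort of up to 24 patients.

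**Working it through.** **1. The plan's own calendar.** A 28-day cycle puts Cycle 2 Day 1 on Day 28 + 1 = 29, as stated. The visit window of 3 days either side gives Days 26 to 32. Section 5 also requires 28 days of therapy, and Section 5.1 takes the longer of 29 days and the visit. The attribution window therefore ends between Day 29 and Day 32, not on Day 26.

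**2. Which onsets are still open at the close.** An event starting on Day t with a criterion of d days is settled on Day t + d. It is open at close day C if t + d > C. Counting onset from Day 2 (first oral doses), there are C − 1 possible onset days, of which d are open. I use d = 7 for at least 7 days, d = 8 for more than 7 days in whole days, and d = 21 for 3 weeks. Uniform onset is my assumption; the documents give no onset distribution.

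| Criterion | Last onset settled by Day 29 | Open onset days, C = 29 | Open onset days, C = 32 | Onset Day 29 is settled on |
|---|---|---|---|---|
| At least 7 days | Day 22 | 7/28 = 25% | 7/31 = 23% | Day 36 |
| More than 7 days | Day 21 | 8/28 = 29% | 8/31 = 26% | Day 37 |
| 3 weeks | Day 8 | 21/28 = 75% | 21/31 = 68% | Day 50 |

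**3. Which clock governs Grade 3 neutropenia.** Table 1 of Section 7.1.4 holds venetoclax until recovery. If that hold counts as a treatment delay, the more-than-7-day criterion is reached well before 3 weeks:

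| First seen | Hold counts as a delay (+8) | Hold does not count (+21) |
|---|---|---|
| Day 15 | Day 23 | Day 36 |
| Day 22 | Day 30 | Day 43 |
| Day 29 | Day 37 | Day 50 |

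On the first reading a Day 15 onset is settled before Cycle 2 Day 1, and the exposed share is about 8 of 28 onset days. On the second it is 21 of 28. The protocol does not say which reading applies.

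**4. Effect on the decision.** One DLT not yet confirmed turns 1/3 into 0/3, so the level is escalated instead of expanded to six. It also turns 2/6 into 1/6, so escalation continues, or the level qualifies as the MTD, where Section 5 would stop.

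**5. Illustration only.** Let p be the true DLT rate and f the fraction of DLTs still open at the decision; the documents give neither. With q = p(1 − f), the probability of escalating is (1 − q)³ + 3q(1 − q)² × (1 − q)³. For p = 0.30 and f = 0 this is 0.343 + 0.151 = 0.494.

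| p | f = 0 | f = 0.10 | f = 0.25 | f = 0.50 |
|---|---|---|---|---|
| 0.30 | 0.49 | 0.56 | 0.65 | 0.81 |
| 0.40 | 0.31 | 0.38 | 0.49 | 0.71 |

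The formula leans high, because an event open in the first three patients would normally be settled before the decision on six. The shares in step 2 must not be read as f.

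**The case against.** A reader might infer that DLT scoring closes at Cycle 2 Day 1 and that the primary endpoint therefore undercounts DLTs. The documents do not support this. Section 5.1 fixes when the event must occur, not when its criterion must be met, and Section 5 ends escalation once two or more patients develop DLT, with no time limit. A late-confirmed event is still a DLT of its dose level. The gap lies in the timing of the decision.

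A reader might also infer that a Day 26 visit permits a decision before the window ends. The 28 days of therapy in Section 5 and the longer-of wording in Section 5.1 speak against that; what remains is a mismatch in wording.

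Several serious toxicities need no waiting at all. Grade 4 neutropenia, febrile neutropenia and any Grade 3 or higher non-hematologic event whose relation to study drug cannot be ruled out are DLTs at once, as is a required platelet transfusion. Read literally, the non-hematologic rule also catches the gastrointestinal and fatigue events despite their own 7-day wording. I therefore rest the point on neutropenia, thrombocytopenia and treatment delay only.

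Finally, there are safeguards in conduct. Section 13.1 has two-weekly data review and weekly meetings, Section 13.5 follows events to resolution or stabilization, and Section 6 allows extra visits. Section 1.5.1 aims at three patients every two months. These make it likely that an open event is known and followed. But none of them makes the escalation decision wait, and the accrual pace is only an intention that gives no slack if the third patient enrolls late.

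**Conclusion.** The gap is real but narrow. Section 5 as written can open the next cohort, or support an MTD declaration, while an event that began in the window is still unsettled. Exposure is mainly to onsets in about the last week: 7 of 28 onset days for Grade 4 thrombocytopenia and about 8 of 28 for treatment delay. Grade 3 neutropenia joins the second group if the venetoclax hold is a treatment delay. The tempting figure of 75% (21 of 28) holds only if it is not, and should not be quoted without that condition.

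These shares rest on uniform onset over Days 2 to 29 and a close on Day 29. They are shares of onset days, not of DLTs; the documents do not allow the fraction of DLTs affected to be estimated. The point should be fixed because one event decides a 3+3 cohort and the remedy is cheap. It does not show that the DLT count is biased by design.

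**What to change.** In Sections 5 and 12, state that the escalation rule and the MTD declaration are not applied while any patient in the cohort has an event that began in the DLT window and whose duration criterion is still open. State also that the event counts at that dose level if the criterion is later met.

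Reconcile these passages as well:
- the evaluation visit at Day 29 with 3 days either side (Section 5), the 28 days of therapy (Section 5) and the window of at least 29 days (Sections 2.1 and 5.1);
- the neutropenia criterion, which presupposes growth factor (Sections 5.1 and 12), and the prohibition of growth factors in the DLT period (Section 8.1.3);
- whether a venetoclax hold under Table 1 of Section 7.1.4 is a treatment delay for DLT purposes, since this determines which clock applies.

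The cost is a few sentences, and a delay only when an event is open: about one week for the 7-day criteria and up to about three weeks for the neutropenia criterion. Sample size is unaffected.

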## **3. OVERALL STUDY DESIGN**

This is a Phase 1b, single-arm, open-label, single-center study of venetoclax (ABT-199) in combination with ibrutinib and rituximab in Subjects with Relapsed/Refractory DLBCL. The trial consists of a dose-escalation of venetoclax in combination with standard doses of ibrutinib and rituximab. For the dose escalation part of the study, a standard 3+3 design will be utilized. Once the MTD has been established, the dose escalation part will be followed by a dose expansion part in a cohort with a maximum of 24 subjects with DLBCL. The purpose of the dose expansion part is to investigate the efficacy of the combination. Between the dose-escalation and dose-expansion, the maximum number of subjects will be 30.

Cycle length will be 28 days. Venetoclax will be administered orally QD, continuously for 24 cycles (from C1D2). Ibrutinib will be administered orally QD, continuously for 24 cycles (from C1D2). Rituximab will be administered IV per institutional standards. weekly X 4 (Cycle 1); once on Day 1 of cycles 2-6 only, then every other cycle until Cycle 24 (total 18 doses of Rituxan from C1D1), Commercially available rituximab IV will be used.

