### **Dose escalation part:**

#### **Study Endpoints**

The primary endpoints for this Phase I study are to determine the MTD, safety, and toxicity of the combination of venetoclax in combination with ibrutinib/rituximab. For this study, cohorts of 3-6 patients are used for each dose level. The dose level in which 2 patients experience unacceptable toxicity is usually considered the MAD. We will define the MTD as the next lower dose level in which no more than 1/6 patients experience unacceptable toxicity. Counts (percentages) of toxicity events will be reported.

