##### Non-Hematologic:

- Any Grade 3 or higher non-hematologic adverse event where relationship to study drug(s) cannot be ruled out (Note: excludes rituximab infusion reactions)
- Grade  $\geq$ 3 nausea, vomiting, or diarrhea uncontrolled by maximal supportive care and persisting greater than 7 days
- Grade 3 fatigue persisting for greater than 7 days
- Treatment delay of any drug greater than 7 days for toxicity

In the Dose Escalation Phase, if a subject is non-compliant with the prescribed therapy or ends treatment within the first cycle for reasons other than study drug(s) related toxicity, ie, withdraws consent, they will be replaced. Any subject that misses  $>4$  doses of ibrutinib or venetoclax for reasons other than toxicity or subject that requires rituximab discontinuation during the first cycle will be replaced. Replaced subjects will be included in the ITT analysis.

There will be no intrapatient dose escalation.

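### Section 5 gives two unreconciled MTD definitions: the one counted over enrolled subjects can accept a level with 2 DLTs after a replacement, and the only one carried into Section 12 is silent if the top level is tolerated

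*Combined protocol and SAP*

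**What the plan says.** Section 2.1 makes the MTD and/or a recommended phase II dose the primary objective. Section 5 (Treatment) then defines the MTD twice in the same passage:

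- **Rule A** steps down from the level that proves too toxic: "We will define the MTD as the next lower dose level in which no more than 1/6 patients experience unacceptable toxicity". Section 12 (Study Endpoints) repeats this sentence, and describes the maximum administered dose (MAD) as follows: "The dose level in which 2 patients experience unacceptable toxicity is usually considered the MAD".
- **Rule B** is a proportion: "The MTD is defined as the highest dose at which <33% of the subjects enrolled in a cohort experience a DLT". It appears only in Section 5.

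Section 5 also says "Dose escalation will cease if 2 or more patients develop DLT". On cohort size it says "If 1 DLT is observed, 3 additional subjects will be enrolled at the same dose level for a total of at least 6 subjects", while Section 12 says "For this study, cohorts of 3-6 patients are used for each dose level".

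Section 12 (DLT Definitions, after the non-hematologic list) replaces escalation subjects who are non-compliant, stop in the first cycle for reasons other than toxicity, miss more than 4 doses of ibrutinib or venetoclax for such reasons, or need rituximab discontinued. It adds "Replaced subjects will be included in the ITT analysis".

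The MTD then drives the rest of the trial. Section 3 says "Once the MTD has been established, the dose escalation part will be followed by a dose expansion part". Section 6 places the expansion cohort, at most 24 patients, at the MTD. Section 12 analyses PFS and OS in the expansion cohort and in those treated at the MTD.

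**The concern.** No sentence gives Rule A or Rule B precedence, and the two are not equivalent. They part in two situations.

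1. **A level with 2 DLTs and more than 6 enrolled.** Rule B divides by subjects enrolled. A replaced subject who had no DLT, if still counted, lowers the proportion without adding safety information. A level that one sentence treats as the MAD, and at which escalation ceases, can then be called the MTD by another sentence in the same passage.
2. **A tolerated top level.** Rule A needs a level above the MTD with 2 toxicities. If the highest planned level passes, there is no MAD and no next lower level, so Rule A returns nothing. Section 12 contains no other definition, yet the opening of expansion and the PFS and OS population both depend on an MTD.

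The first can produce conflicting dose decisions from the same data. The second leaves the statistical section without an endpoint result in a plausible outcome.

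**Working it through.** **Plan's own figure.** Section 12 gives at most 12 escalation patients: 2 levels x 6 = 12. It reproduces. It leaves no room for replaced subjects at two full levels, so the sample size does not foresee a level with more than 6 enrolled, although the replacement rule permits one.

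**Rule B with 2 DLTs**

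| Enrolled at the level | 2 DLTs as % | Below 33%? |
|---|---|---|
| 3 | 66.7 | no |
| 4 | 50.0 | no |
| 5 | 40.0 | no |
| 6 | 33.3 | no |
| 7 | 28.6 | yes |
| 8 | 25.0 | yes |
| 9 | 22.2 | yes |

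Within 3-6 patients, no outcome with 2 DLTs passes, so the two rules agree there. The conflict needs at least 7 enrolled. (3 DLTs pass only from 10 enrolled: 3/10 = 30%.)

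**Inputs that must be assumed.** The documents give no DLT rate by level and no replacement rate. I take DLT rates at levels 1/2 of 10/20%, 15/25% and 20/35%, and add 10/10% and 10/30%. The 10% and 30% are the expected and unacceptable toxicity rates in Section 12 (Stopping Guidelines), which are stated there for the expansion cohort. Replacement is 10% or 15% per subject, independent of DLTs, and replaced subjects contribute no DLT. Any second group of three is enrolled in full, and the top level is filled to 6, as Section 5 requires for the MTD or highest tested dose.

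**Formulas.** Let b(x; p) be the binomial probability of x DLTs in 3 patients.

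- Level 1 passes: C = b(0; p1) + b(1; p1) b(0; p1)
- Exactly 2 DLTs in 6 at level 2: T = b(1; p2)^2 + b(0; p2) b(2; p2)
- At least one replacement in filling 6 places: R = 1 - (1 - r)^6, which is 0.469 at 10% and 0.623 at 15%
- At most 1 DLT in 6 at level 2: U = b(0; p2)[b(0; p2) + b(1; p2)] + b(1; p2) b(0; p2)

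**Situation 1: C x T x R.** For 10/20%: C = 0.729 + 0.243 x 0.729 = 0.906; T = 0.384^2 + 0.512 x 0.096 = 0.197; C x T = 0.178; times R = 0.084 and 0.111.

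| DLT rates, levels 1/2 | C | T | C x T | 10% replaced | 15% replaced |
|---|---|---|---|---|---|
| 10/20% | 0.906 | 0.197 | 0.178 | 0.084 | 0.111 |
| 15/25% | 0.814 | 0.237 | 0.193 | 0.090 | 0.120 |
| 20/35% | 0.709 | 0.262 | 0.186 | 0.087 | 0.116 |
| 10/10% | 0.906 | 0.079 | 0.071 | 0.033 | 0.044 |
| 10/30% | 0.906 | 0.259 | 0.235 | 0.110 | 0.146 |

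The first three scenarios give about 8-12%. The last two extend the range to about 3-15%. All hold only if replaced subjects count as enrolled.

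**Situation 2: C x U.**

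| DLT rates, levels 1/2 | C | U | C x U |
|---|---|---|---|
| 10/10% | 0.906 | 0.886 | 0.80 |
| 10/20% | 0.906 | 0.655 | 0.59 |
| 10/30% | 0.906 | 0.420 | 0.38 |

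In each of these outcomes Rule B points to level 2, and Rule A, read literally, names no level.

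**The case against.** The strongest reply is that Section 5, read as a whole, works. Rule A describes what follows once a MAD has been found. If none is found it is silent; it does not name a lower dose. Rule B, the provision that escalation may end when the highest level has been tested, the requirement for 6 subjects at the MTD or highest tested dose, and the and/or wording of the objective all point to level 2. On this reading no patient would receive a different dose because of situation 2.

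On situation 1, the rules agree for every cohort size that Section 12 plans. Section 5 applies the escalation rules only after 3 subjects have completed the DLT period. Replaced subjects are placed in the ITT analysis, which is not said to be the dose decision. Escalation also ceases at 2 DLTs.

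Much of this stands. A reader might infer that Section 12 would select 400 mg where Section 5 selects 800 mg; the documents do not support that, because Rule A then selects nothing. Nor is it a contest between Section 5 and Section 12, since Section 5 contains both rules. A reader might also call 2 DLTs under Rule B a likely outcome; it needs at least 7 enrolled, exactly 2 DLTs in the usual case, and replaced subjects in the denominator.

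What the reply does not remove is the missing order of precedence. Rule B says enrolled, not evaluable; no DLT-evaluable set is defined; and ceasing escalation at 2 DLTs does not stop Rule B from naming that same level the MTD. Nor does any sentence say outright that a tolerated top level becomes the MTD or the recommended phase II dose.

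**Conclusion.** The concern holds in a limited form: Section 5 has two MTD definitions, Section 12 repeats one, and neither is given precedence.

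- **2-DLT conflict:** real but less common. It arises at level 2 in about 8-12% of trials under DLT rates of 10/20% to 20/35% and 10-15% independent replacement, and only if replaced subjects stay in the denominator, which the documents leave open. This is the part that could change a dose decision.
- **Tolerated top level:** a common outcome under the assumed rates (about 0.80, 0.59 and 0.38), but the consequence is a gap in Section 12. Those figures are the chance of meeting the gap, not the chance of choosing a different dose.

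This should be corrected, because the MTD is the primary endpoint and sets the dose for up to 24 expansion patients. It does not show that the escalation design is unsound.

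**What to change.** Three changes to the text:

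1. Reconcile the two sentences in Section 5 with the one in Section 12, so that a single MTD definition stands in both. Which dose-selection rule governs is for the sponsor to decide.
2. Define a DLT-evaluable set and use it, in place of subjects enrolled, as the denominator for the dose decision. Replaced subjects are left out of that decision, so that replacement cannot dilute the DLT proportion; they can remain in the ITT analysis as planned.
3. State in Section 12 what applies when no level has 2 DLTs, including which label (MTD or recommended phase II dose) the opening of expansion and the PFS and OS population then refer to.

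Cost: two or three sentences, no extra patients and no change to the cohort scheme.
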